5.9 Protocol deviations

A protocol deviation is any change, divergence, or departure from the study design or procedures defined in the clinical protocol. Protocol deviations will be classified by medical review prior to primary analysis and critical and major protocol deviations will be identified. A critical protocol deviation is a deviation that adversely affects data integrity, patient's right and safety. A major protocol deviation is a deviation that potentially can affect data integrity, patient's right and safety. All critical and major deviations related to trial inclusion or exclusion criteria, conduct of the trial, patient management or patient assessment will be described in the clinical study report.

The Sponsor or designee is responsible for producing the final protocol deviation file. This file will include a description of each protocol deviation and whether or not this deviation is classified as a critical or major protocol deviation. This file will be finalized prior to performing the primary analysis.

5.10 Derived analysis visit windows

A scheduled measurement will be used if it is available. Otherwise, derived analysis visit window will apply to data collected on scheduled visits and early withdrawal visits (such as PD, clinical laboratory parameter, vital signs, etc) to re-allocate a post-baseline unscheduled measurement to a scheduled measurement, except for PK and ECG, using Study Day (defined in [Section 5.2](#)), according to the following allocation table:

Analysis visit label	Target study day	Derived Window in study days	
		lower bound	upper bound
Baseline	1	-INF	1
Day 15	15	2	21
Day 29	29	22	35
Day 43	43	36	49
Day 57	57	50	70
Day 85	85	71	98
Day 113	113	99	126
Day 141	141	127	154
Day 169	169	155	182
Day 197	197	183	210
Day 225	225	211	238
Day 253	253	≥239	Actual EOS/ET visit date if EOS/ET visit is ≥239
Day 281	28 days after EOS/ET for patients who complete the AT F/U visits	1 day after EOS/ET visit	999
Endpoint	Last non-missing post-baseline assessment on or before EOS/ET visit		

If more than one data point is within a window the visit closest to the target study day will be selected. If there are multiple visits with the same distance from the scheduled visit day, the last value will be selected.

5.11 Geographic region

Geographic region will consist of the following categories: North America, Europe, Asia, Other. The countries in each region are the following:

- North America (United States)
- Europe (Bulgaria, Denmark, France, Germany, Hungary, Italy, Portugal, Spain, Turkey, Ukraine, United Kingdom)
- Asia (China, India, Japan, Korea, Malaysia, Taiwan)
- Other (Australia, Israel, South Africa)

6 STATISTICAL ANALYSES

6.1 Patient disposition

Patient disposition will be tabulated for the following categories:

- patients screened
- patients screen failed
- patients randomized
- patients in each analysis population
- patients treated (fitusiran arm only)
- patients who completed the study treatment (9-month treatment period, fitusiran arm only)
- patients who discontinued study drug and primary reasons for study drug discontinuation (fitusiran arm only)
- patients who discontinued study drug and primary reasons for study drug discontinuation due to Covid-19 (fitusiran arm only)
- patients who completed the study
- patients who withdrew prior to completing the study but completed Month 9 visit
- patients who withdrew prior to completing the study and primary reasons for withdrawal.
- Patients who withdrew prior to completing the study and primary reasons for withdrawal due to Covid-19

Patient disposition will be presented by randomized treatment arm and overall, as applicable.

Patients randomized by country, site and randomization stratification factor stratum will be summarized by randomized treatment arm and overall.

6.2 Demographics and baseline characteristics

Demographic and baseline characteristics, baseline disease characteristics, and medical history information will be summarized by treatment arm and overall for the ITT analysis set, safety analysis set (if different from the ITT analysis set), and the per-protocol analysis set. No formal statistical comparisons will be performed.

Age, height, weight, and body mass index (BMI) will be summarized using descriptive statistics. Age group, sex, race, ethnicity, and region will be summarized by presenting the numbers and percentages of patients in each category.

The following baseline disease characteristics will be summarized: age at diagnosis, time from diagnosis to randomization, hemophilia type, and number of bleeding episodes in the last 6 months prior to the study.

6.3 Efficacy analysis

Bleeding Episode Definitions

The primary source of bleeding data will be the eDiary. Additional bleeding data may be captured from the bleeding diary pages of the CRF, if not reported in the eDiary. Any other sources of bleeding data will be discussed in the CSR.

A bleeding episode is defined as any occurrence of hemorrhage that may require administration of BPA or factor. A traumatic bleeding episode is one that is caused by a known injury or trauma. Bleeding episodes sustained during sports and recreation will be counted as traumatic bleeding episodes.

Bleeding or any symptoms of bleeding at the same location that occur within 72 hours of the last injection used to treat a bleed or 72 hours after an untreated bleed at that location will be considered a part of the original bleeding event, and will count as one bleeding episode. Any bleeding symptoms that begin more than 72 hours from the last injection used to treat a bleed or 72 hours after an untreated bleed at that location will constitute a new bleeding event.

Traumatic bleeds that occur in different locations simultaneously (same date/time) in the same patient will be considered as one bleeding episode. Spontaneous bleeds that occur simultaneously (same date/time) in different locations in the same patient will be considered as separate bleeds.

Efficacy analysis will focus on observed data as collected, unless otherwise specified. Patients who discontinue study drug during the study will be strongly encouraged to continue study participation including the recording of bleeding episode data. Only bleeding episodes that are treated will be include in the primary analysis of endpoints evaluating bleeding.

Efficacy Period and Treatment Period

In the protocol, for the purpose of ABR calculation, fitusiran “Onset Period”, “Efficacy Period” and “Treatment Period” are defined. The Onset Period is defined as the first 28 days after the first dose of fitusiran, during which the AT lowering capacity of fitusiran is increasing but has not yet reached therapeutic levels. The Efficacy Period is defined as starting on Day 29 when the AT lowering capacity of fitusiran has achieved therapeutic target range. The Treatment Period is defined as the onset period plus the efficacy period. The window for each period is summarized in the table below. The corresponding window is applied to on-demand arm for analysis purpose.

	Fitusiran arm/On-demand arm
Onset Period	Day 1 to the earlier of Day 28 and the last day of bleeding follow up
Efficacy Period	Day 29 to the earliest of (Day 246, or the last day of bleeding follow up)

Treatment Period	Onset period plus the efficacy period
------------------	---------------------------------------

The last day of bleeding follow up is defined as the deactivation date captured in eDiary.

If a patient does not have bleeding episode data collected after Day 28 due to early study discontinuation, the efficacy period will be from Day 1 to the earlier of date of study discontinuation and the last day of bleeding follow up.

The onset period, efficacy period and treatment period also exclude the period of following intercurrent events to avoid confounding of treatment effect for the primary efficacy analysis based on On-Treatment Strategy.

- After one month (28 days) from fitusiran treatment discontinuation in the fitusiran efficacy period. Excluding bleeding data after one month from fitusiran treatment discontinuation is considered reasonable and adequate considering that fitusiran is dosed monthly and EOS is one month after last dose of fitusiran.
- Perioperative period of major surgery. The perioperative period is defined as the day of the surgery through the final day on which supplemental hemostatic or antithrombotic treatments are administered as part of the perioperative treatment plan.
- Period of minor surgery is defined as the Perioperative period of surgery above or to 72 hours from the end of surgery, whichever is later.
- Period of Antithrombin treatment is defined as the first day of antithrombin treatment through the final day on which antithrombin or other anticoagulant therapies are administered plus 5 half-lives of that specific product.
- After prophylactic treatment with emicizumab, BPA or factor.

The summary statistics for number of patients who are lost-to-follow-up and who had each intercurrent event will be provided.

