7.2.1. Electronic Diary

Patients will be issued an eDiary to record all bleeding events and all doses of factor concentrates administered during the conduct of the study. Entries are to be made in a timely manner, and it is preferred that doses are entered immediately upon administration or within 24 hours. Patients will be prompted to enter bleeding location, severity, causality (spontaneous or traumatic), doses of factor concentrates, and reasons for dosing (prophylaxis, treatment of a bleed, and preventive dose for anticipated activity). Training of patients should be documented in the appropriate source record.

The Sponsor or an independent delegate will review diary entries for data quality to identify issues such as subjects who may need retraining on diary use and timely entry of bleeding episode information.

Bleeding episodes will be recorded by the patient in the eDiary, and reviewed by the Investigator (and Sponsor or independent delegate) continuously for the study duration. The site will contact the patient at a minimum interval of every 2 weeks per schedule of assessments to review diary records and ensure that the patient is utilizing the device appropriately.

Sites will be notified when patients enter initial treatments for bleeding events into their eDiaries. If the dose amount exceeds the recommended dose according to the bleeding management plan, the patient must be contacted as soon as possible, preferably within 24-48 hours of receiving the alert. At the time of contact the patient's clinical condition will be reviewed along with the dose and efficacy of the treatment given, and the Investigator will provide appropriate guidance regarding further management of the bleeding episode. The site will also receive an alert, and must make contact with the patient as soon as possible if a third dose of product is administered for a single bleed, to review clinical condition, the need for further therapy, and appropriate ongoing management of the bleeding episode required to achieve hemostasis.

In addition, patients will be instructed to contact the site if they feel they need to administer factor concentrates at a higher dose level or higher frequency than their bleeding management plan recommends, or if more than two doses are required to achieve hemostasis.

Complete instructions will be provided in the Study Manual.

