6.3.1 Primary endpoint

6.3.1.1 Primary efficacy analysis based on on-treatment strategy

The primary objective of this study is to assess the efficacy of fitusiran on prevention or reduction of bleeding. Including bleeding events in the period of intercurrent events such as use of prophylactic medication or surgery or after fitusiran treatment discontinuation could significantly bias fitusiran effect and make the comparisons difficult to interpret. The on-treatment strategy is considered of greatest relevance in assessing this primary objective (ICH E9 (R1), 2018). The primary efficacy analysis population will be the ITT Analysis Set as defined in [Section 4](#).

Global Protocol

The number of bleeding episodes will be annualized for each patient using the following formula:

$$\text{Annualized bleeding rate (ABR)} = \frac{\text{total number of bleeding episodes}}{\text{total number of days in the respective period}} \times 365.25.$$

The primary efficacy analysis will include all bleeding episodes occurring in the efficacy period.

Let λ_F represent the ABR for fitusiran arm and λ_O represent the ABR for on-demand arm. The null and alternative hypotheses of the primary analysis, respectively, can be written as follows:

$$H_0: \frac{\lambda_F}{\lambda_O} = 1 \quad H_A: \frac{\lambda_F}{\lambda_O} \neq 1$$

An estimated ABR ratio $\frac{\lambda_F}{\lambda_O} < 1$ and two-sided p-value < 0.05 from the significance test will lead to the rejection of H_0 in favor of H_A ; it will be concluded that prophylactic use of fitusiran reduces the frequency of bleeding episodes compared to the on-demand therapy.

The ABR ratio λ_F/λ_O will be estimated using a negative binomial model:

$$\begin{aligned} & \log(\text{number of bleeding episodes}) \\ &= \beta_0 + \beta_1 \cdot \text{Treatment} + \beta_2 \cdot \text{ABR}_0 + \beta_3 \cdot \text{Hemophilia type} + \log(\text{duration}). \end{aligned}$$

The number of bleeding episodes is the response variable. The treatment arm, randomization strata of number of bleeding episodes in the 6 months prior to study entry (ABR_0) and randomization strata of hemophilia type are treated as fixed effects. The logarithm of the duration (in years) that each patient spends in the efficacy period matching the bleeding episode data being analyzed is included as an offset variable to account for unequal follow-up time due to early withdrawal, surgery, etc.

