The number of bleeding episodes is the response variable. The treatment arm, randomization strata of number of bleeding episodes in the 6 months prior to study entry (ABR_0) and randomization strata of hemophilia type are treated as fixed effects. The logarithm of the duration (in years) that each patient spends in the treatment period matching the bleeding episode data being analyzed will be included as an offset variable to account for unequal follow-up time due to early withdrawal, surgery, or etc.

The ratio of ABR in the fitusiran treatment arm to the on-demand arm, its 95% CI, and the p-value for the hypothesis above will be presented. The estimated mean ABRs in the 2 treatment arms along with their 95% CIs from the model will be presented. In addition, median and interquartile range (Q1, Q3) for the observed ABR will be summarized descriptively by treatment arm.

Given that the primary analysis is based on on-treatment strategy, primary and secondary bleeding-related data during the efficacy and treatment periods are expected to be complete. No sensitivity analysis about the missing data mechanism will be performed.

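### Bleeding follow-up ends at eDiary deactivation, and the study-discontinuation cap covers only patients without data after Day 28; it should cover every patient

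*SAP*

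**What the plan says.** SAP 6.3 sets the efficacy period as "Day 29 to the earliest of (Day 246, or the last day of bleeding follow up"), and the treatment period as the onset period plus the efficacy period. The last day of bleeding follow-up has one definition: "The last day of bleeding follow up is defined as the deactivation date captured in eDiary".

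One group gets a further limit. For patients who left the study early and have no bleeding data after Day 28, the rule reads: "the efficacy period will be from Day 1 to the earlier of date of study discontinuation and the last day of bleeding follow up".

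SAP 6.3 also removes certain time from the on-treatment analysis. For the fitusiran arm this includes time "After one month (28 days) from fitusiran treatment discontinuation in the fitusiran efficacy period". The on-demand arm has no matching exclusion.

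The resulting length is the model offset. SAP 6.3.1.1 describes it as "The logarithm of the duration (in years) that each patient spends in the efficacy period matching the bleeding episode data being analyzed". For the treatment-policy analysis, SAP 6.3.1.2 treats bleeds after study discontinuation as uncollected and imputes them. Neither document says when or by whom an eDiary is deactivated.

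**The concern.** The SAP takes the earlier of two dates for the earliest leavers. That wording is needed only if deactivation can come after study discontinuation. A patient who leaves on, say, Day 100 faces the same possibility but is not given the cap.

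For such a patient, any days between leaving and deactivation count as follow-up, while no bleeds from those days reach the numerator. The same days would be observed time under SAP 6.3 and missing time under SAP 6.3.1.2. They would also not be duration matching the data being analysed, which is what SAP 6.3.1.1 asks for.

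The rule sets the denominator of the primary endpoint and of every other bleeding rate, so at stake are the reported ABRs, their ratio and its confidence interval. Other provisions do not catch it. SAP 5.8 deals with incomplete entries, not with stretches without observation. The multiple imputation in SAP 6.3.1.1 is for patients without data after Day 28. Under the US Protocol text of that section, "No sensitivity analysis about the missing data mechanism will be performed".

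**Working it through.** **The plan's own figures.** SAP 5.1 assumes mean ABR 18 (SD 14) on demand and 4 (SD 6) on fitusiran, with 32 and 64 evaluable patients and two-sided alpha 0.05.

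- Log rate ratio: ln(4/18) = −1.504.
- Standard error: √[14²/(18² × 32) + 6²/(4² × 64)] = √(0.0189 + 0.0352) = 0.2325.
- z = 1.504/0.2325 = 6.47, so power is above 99.9%. The stated figure of more than 90% holds.
- Randomized total: 96/0.80 = 120, as stated.

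**One patient.** Suppose he leaves the study on Day 100 (100 − 28 = 72 efficacy days observed). Both lags below are assumed.

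- Deactivated 28 days later: 72/100 = 0.72. A true ABR of 18 reads 12.96.
- Deactivated 60 days later: 72/132 = 0.545. For a fitusiran patient who stopped dosing when he left, the 28-day cut limits the factor to 0.72.

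**Arm level.** The efficacy period is at most 246 − 29 + 1 = 218 days. Assume that 20% leave (the SAP's drop-out figure), uniformly over those days, and that each device is deactivated L days later.

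- Mean observed days: 0.8 × 218 + 0.2 × 109 = 196.2.
- Mean extra days per leaver, capped at Day 246: L − L²/436.
- Factor on the arm's person-time rate: 196.2 / [196.2 + 0.2 × (L − L²/436)].

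For fitusiran, L is limited to 28 days, taking treatment and study discontinuation as the same day.

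| Assumed lag | On-demand factor | On-demand ABR | Fitusiran factor | Fitusiran ABR | Ratio (design 0.222) |
|---|---|---|---|---|---|
| 14 days | 0.986 | 17.75 | 0.986 | 3.95 | 0.222 |
| 30 days | 0.972 | 17.50 | 0.974 | 3.90 | 0.223 |
| 60 days | 0.950 | 17.10 | 0.974 | 3.90 | 0.228 |

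At 60 days the ratio rises by 0.974/0.950 − 1 = 2.5%. With 10% drop-out the 60-day factors are 0.976 and 0.988, about half the effect.

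**Start of the 28-day clock.** If treatment discontinuation means the last dose, with dosing every 28 days, the fitusiran factor at 60 days is 0.986. The ratio then rises by 0.986/0.950 − 1 = 3.8%. So 2.5% is not an upper limit. In standard errors the two shifts are ln(1.025)/0.2325 = 0.11 and ln(1.038)/0.2325 = 0.16.

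**Outer case.** If devices of on-demand leavers stay active to Day 246, that arm's factor is 196.2/218 = 0.900. With fitusiran at 0.974 the ratio is 0.222 × 0.974/0.900 = 0.240. Simulating the negative binomial model with a log-duration offset (40 and 80 patients, treatment effect only, 200 runs) gave 0.243, and all runs were significant.

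**Small subgroups.** SAP 6.3.1.4 fits the model with as few as 3 patients per arm. One on-demand patient with 72 days counted as 132, beside two completers, gives (218 + 218 + 72)/(218 + 218 + 132) = 508/568 = 0.894. That lowers the arm's person-time rate by 11%.

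**The case against.** **The miscount is conditional.** It arises only if deactivation follows study discontinuation, and the documents give no timing. Instructions may stand in the Study Manual, which is not among the documents. A reader might infer that unobserved days are in fact being counted as bleed-free. The text does not show that. It shows a rule that would do so if the lag exists, and a cap elsewhere in the SAP that allows for it. The diary also records events, so a day without an entry is not by itself an unobserved day.

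**Supervision shortens gaps.** Protocol 7.2.1 states: "The site will contact the patient at a minimum interval of every 2 weeks per schedule of assessments to review diary records". A 60-day lag would span about four such contacts, so it is an upper-end assumption. This stands, but the SAP does not use contact dates to end follow-up.

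**Few patients are touched.** The end-of-study visit is at Day 253 ± 7 and follow-up is cut at Day 246, so completers with an active device are unaffected. This stands.

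**CRF pages.** SAP 6.3 also says: "Additional bleeding data may be captured from the bleeding diary pages of the CRF, if not reported in the eDiary". A reader might infer that bleeds entered on CRF pages after deactivation are lost. They are not: inclusion depends on when the bleed occurs, so one with onset before deactivation still counts. One with onset later drops out together with its days, which loses information but does not in itself bias the rate.

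**Other analyses help in part.** The SAP tabulates patients lost to follow-up, and the treatment-policy imputations start at study discontinuation. They do not correct the offset of the primary analysis.

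**Conclusion.** The concern holds as a gap in the follow-up rule, worth closing because closing it costs almost nothing. Whenever deactivation follows study discontinuation in a patient with data after Day 28, SAP 6.3 overstates his person-time and contradicts SAP 6.3.1.2.

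The size is small at arm level: about 1.4% to 5.0% on the on-demand ABR and 1.4% to 2.6% on the fitusiran ABR (less if the 28-day clock starts at the last dose). This rests on assumed lags of 14 to 60 days and 20% uniform drop-out. Single patients and very small subgroups can be affected more.

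A reader might infer that the rule flatters fitusiran. With the same lag in both arms it does not: the 28-day cut shortens the excess in the fitusiran arm only, so the ratio is unchanged or moves toward the null. The direction is not guaranteed if lags differ. A 28-day lag in the fitusiran arm alone would give 0.222 × 0.974 = 0.216. At the design effect the primary success decision did not change in any scenario examined.

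**What to change.** In SAP 6.3, define the last day of bleeding follow-up for all patients and all bleeding endpoints as the earlier of the eDiary deactivation date and the date of study discontinuation. This is the rule the SAP already uses for patients without data after Day 28. It also makes the offset agree with the point at which SAP 6.3.1.2 treats data as missing.

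The cost is one sentence before database lock. Study discontinuation is already recorded in the eCRF (Protocol 5.3.2), so no new data are needed. The downside is that a few days of person-time are lost for some early leavers. Ending follow-up at the last site contact is not advised, because it could delete up to two weeks of genuine diary data.
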